- On therapy with aspirin(<100mg/day) and clopidogrel (75mg/day) for at least 30 days per standard of care
- 3) Age between 18 and 80 years old

Exclusion Criteria

- 1) History of intracranial bleeding
- 2) Known hepatic impairment (based on clinical judgment)
- 3) Active bleeding or propensity to bleed or blood dycrasia
- 4) Platelet count $< 80 \times 10^6 / \text{mL}$
- 5) Hemoglobin <10g/dL
- 6) Hemodynamic instability
- 7) Estimated glomerular filtration rate (eGFR) <30 mL/min
- 8) On treatment with oral anticoagulants
- 9) Patients with sick sinus syndrome (SSS) or II or III degree AV block without pacemaker protection

[figure not shown]
- 10) Drugs interfering CYP3A4 metabolism (to avoid interaction with ticagrelor): ketoconazole, itraconazole, voriconazole, clarithromicin, nefazodone, ritonavir, saquinavir, nelfinavir, indinavir, atazanavir and telithromizycin
- 11) Pregnant females [women of childbearing age must use reliable birth control (i.e. oral contraceptives) while participating in the study].

Research design

Patients meeting inclusion criteria will be enrolled in this prospective, randomized, openlabel study. Baseline labs obtained within the past 180 days will be considered valid for screening purposes. If baseline labs are not available, these will need to be obtained prior to considering a patient eligible for study entry (patients will have 90 days to enter the study). Eligible patients will undergo a 7±2 day run-in phase with ticagrelor after switching from clopidogrel 75mg/day to ticagrelor 180mg LD followed by 90mg bid MD. Ticagrelor dosing in this study is line with FDA recommendations [15]. After this run-in phase, patients will be randomized (1:1:1:1) into one of the four following groups: A) clopidogrel 600 mg LD 24 hours after last MD of ticagrelor, followed by 75mg daily MD; B) clopidogrel 600 mg LD 12 hours after last MD of ticagrelor, followed by 75mg daily MD; C) clopidogrel 75mg daily MD 24 hours after last MD of ticagrelor; D) continue ticagrelor MD 90mg twice daily. The FDA approved dose for clopidogrel is 300 mg loading dose and 75 mg/qd maintenance dose; however standard of care loading dose is 600 mg which is in line with practice guidelines [1-5].

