Blood sampling: Peripheral venous blood samples (20 mL) will be drawn through a short venous catheter inserted into a forearm vein and collected in citrate, EDTA, and serum tubes as appropriate for assessments. The first 2-4 mL of blood will be discarded to avoid spontaneous

platelet activation. Blood sampling for PD will be performed at the following time points: prior to run-in baseline visit (24 hours after last clopidogrel dose in order to assess trough levels of platelet reactivity), after run-in (12 hours after last ticagrelor maintenance dose of run-in period), 24 hours after washout (groups A and C only), and 2, 24, 48, 72 hours and 10±3 days after randomization. For patients randomized to groups A and C, both requiring 24 hours washout from last MD, they will take their morning MD of ticagrelor after blood sample collection for their post-run-in phase and return the following morning to receive the randomized treatment (these groups will have a total of 8 blood sampling time points). Patients randomized to groups B and D will initiate their randomized treatment the same morning of the post-run-in phase visit (these groups will have a total of 7 blood sampling time points). CYP2C19 genetic status will be evaluated at baseline visit. PD assessment will include VerifyNow point-of-care testing (VN-P2Y₁₂), light-transmittance aggregometry (LTA) and whole blood vasodilator-stimulated phosphoprotein (VASP) as described below. Time points will have a $\pm 10\%$ window. Results of genetic testing will not be used for clinical decision makings on choice of antiplatelet treatment regimen to be used at the end of the study. This is because we are studying patients in stable clinical conditions who have already on maintenance clopidogrel therapy without experiencing ischemic events, which are more likely to occur in the earlier phases of treatment in the setting of PCI [10]. Moreover, routine genetic testing and modification of treatment based on results of genetic testing is a class III recommendation in practice guidelines [1,2]. An illustration of the study design is provided below. A study table summarizing protocol procedures is provided as an appendix.

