antibodies by flow cytometry with the Platelet VASP-FCM kit (Biocytex Inc., Marseille, France) as previously described [19]. PGE1 increases VASP-P levels by stimulation of adenylate cyclase. Binding of ADP to P2Y₁₂ leads to Gi-coupled inhibition of adenylate cyclase. Therefore, the addition of ADP to PGE1-stimulated platelets reduces PGE1-induced VASP-P levels. If P2Y₁₂ receptors are successfully inhibited by inhibitors, addition of ADP will not reduce the PGE1-stimulated VASP-P levels. The platelet reactivity ratio (PRI) will be calculated after measuring VASP-P levels after stimulation with PGE1 (MFI PGE1) and also PGE1 + ADP (MFI PGE1 + ADP). The P2Y₁₂ reactivity ratio = ([MFI PGE1] – [MFI PGE1 + ADP]/[MFI PGE1]) x 100%.

4) CYP 2C19 Genetic testing: CYP2C19 genetic status will be performed with the Spartan RX point-of-care rapid genotyping device. Spartan RX (Spartan Bioscience Inc., Ontario, Canada) is a point-of-care determining the CYP2C19 (*1,*2,*3,*17) allele status within 1 hour [20]. This test consisted of four separate steps intended to be done in less than 8 minutes: acquisition of a buccal swab; insertion of the swab into the cartridge; insertion of the reaction solution into the device; and analysis of CYP2C19 genotype triggered by a button on the device. In particular, this point-of-care assay enables assessment of the following alleles: *1,*2,*3 and *17. The most common LOF alleles are *2 and *3. Therefore, carriers of *2 or *3 LOF carrier status can be homozygotes (*2/*2, *3/*3 or *2/*3) or heterozygotes (*1/*2, *1/*3, *2/*17, *3/*17). Non-carriers of LOF alleles include the following: *1/*1, *1/*17 or *17/*17.

Definitions of high on treatment platelet reactivity

High on-treatment platelet reactivity (HPR) will be defined according to updated expert consensus as following: PRU higher than 208 or 235, MPA-ADP (5 μ M) >46%, MPA-ADP (20 μ M) >59% and VASP-PRI >50% [21,22].

Study endpoints and sample size calculation

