The primary endpoint is the comparison of PRU assessed by VN- P2Y₁₂ at 48 hours after switching from ticagrelor 90 mg bid to clopidogrel 600 mg LD given 24 hours after last ticagrelor MD (group A) vs. clopidogrel 75 mg MD given 24 hours after last ticagrelor MD (group C). We hypothesize that switching from ticagrelor to clopidogrel with a loading dose will have less increase in platelet reactivity than that without loading dose and the sample size was determined based on the objective of establishing superiority of this approach. Superiority will be assessed using a 95% confidence interval (CI) of the difference in mean PRU between these two groups. Under the assumption of a mean difference of 60 PRU between groups and a common standard deviation of 50 PRU, a sample size of 16 per group allows for the 95% CI with a 95% power and alpha=0.05. Considering 4 arms of treatment and a possible invalid data in 20-25% of patients due to technical issues or drop-outs, we will randomize up to a total of 80 patients to ensure complete data. We anticipate screening 100 patients to identify these 80 patients to be randomized. Secondary endpoints include comparison of PRU (other than primary endpoint) assessed by VN-P2Y₁₂, 5 and 20 µM ADP aggregation assessed by LTA and VASP-PRI in all four groups at each time points; rates of HPR according to each platelet function assay

(VN-P2Y₁₂, LTA, and VASP-PRI) in all four groups at each time point; impact of CYP2C19 LOF genetic status on PD parameters.

Statistical analysis plan

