Continuous variables will be expressed as a mean \pm SD when are normally distributed or median [IQR] when are not normally distributed. Categorical variables will be expressed as frequencies and percentages. The Kolmogorov-Smirnov test will be used to examine data distribution normality. Comparisons between categorical variables will be performed using twotailed Fisher's exact test or the Pearson's chi-square test. Student's t test, Mann-Whitney U-test and Wilcoxon test will be used to compare continuous variables when appropriate. A repeated measures analysis of variance (ANOVA) model will be used to evaluate intra-group comparisons and the overall difference between groups. An analysis of covariance (ANCOVA) method with a general linear model, using the baseline value of platelet reactivity as a covariate, will be used to evaluate all between-groups comparisons. Missing data will not be imputed. A 2-tailed p value of < 0.05 is considered to indicate a statistically significant difference for all the analyses performed. Statistical analysis will be performed by our group using SPSS v22.0 software (SPSS Inc. Chicago, IL).

Possible Discomforts and Risk

The study entails blood draws at multiple time points as indicated above. The risks of the blood draw may include faintness, inflammation of the vein, pain, bruising or bleeding at the site of the puncture. There is also a slight risk of infection from the blood draw. In clinical trials, the

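### The between-arm HPR comparisons are unadjusted although HPR status on chronic clopidogrel is measured at V1 in every group; the comparison is unbiased but gives up precision and power

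*Combined protocol and SAP*

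**What the plan says.** - **Entry.** Inclusion Criteria require "clopidogrel (75mg/day) for at least 30 days per standard of care". No inclusion or exclusion criterion concerns platelet reactivity.
- **V1 measurement.** Under Research design, the pre-run-in sample is taken "24 hours after last clopidogrel dose in order to assess trough levels of platelet reactivity". Table S1 marks this PD test for all four groups.
- **Allocation.** After the ticagrelor run-in, "patients will be randomized (1:1:1:1) into one of the four following groups". No stratification factor is named.
- **Endpoint.** Study endpoints and sample size calculation lists "rates of HPR according to each platelet function assay" in all four groups at each time point, as a secondary endpoint. HPR is a status above a cut-off; for VerifyNow this is "PRU higher than 208 or 235".
- **Test.** The Statistical analysis plan states: "Comparisons between categorical variables will be performed using twotailed Fisher's exact test or the Pearson's chi-square test". It also provides an ANCOVA with a general linear model, "using the baseline value of platelet reactivity as a covariate, will be used to evaluate all between-groups comparisons". It does not say how a binary HPR outcome would be adjusted, or which visit is the baseline. Table S1 applies that word to V1 (run-in baseline) and to the PD samples at V2 and V3.

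**The concern.** Groups A, B and C all go back to the drug the patients were taking at V1. A patient above the HPR cut-off on chronic clopidogrel may well be above it again once ticagrelor has worn off, with or without a loading dose. V1 HPR status is therefore a plausible strong predictor of the outcome. It is measured before randomization, with the same assays, and the categorical tests ignore it.

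Two things are at stake. First, in arms this small, chance differences in V1 HPR add noise to the HPR contrast that an adjusted analysis would remove. Second, the Background section raises a rebound in reactivity as a possible effect of switching away from ticagrelor. A crude post-switch HPR rate within an arm does not show whether the patients counted are new to HPR or have returned to where they were at V1. The gap to group D, which stays on ticagrelor, has the same limitation.

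**Working it through.** **The plan's own figures.** No sample size or power is given for HPR. The only calculation is for mean PRU, A against C: 2 × (50/60)² × (1.645 + 1.645)² = 15.03, so 16 per group. This reproduces the plan with a one-sided alpha of 0.05; a two-sided alpha gives 2 × (50/60)² × (1.960 + 1.645)² = 18.05, so 19, which is a separate matter. Randomizing 80 gives 80/4 = 20 per arm, and 20% loss leaves 20 × 0.80 = 16. The checks below use 16 and 20.

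**Step 1: chance imbalance in V1 HPR.** The V1 rate p is not in the documents; the range 20% to 50% is assumed. The SD of the between-arm difference is √(2p(1−p)/n), and the gap probabilities are exact binomial.

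| V1 HPR (assumed) | SD, n = 16 | P(gap ≥ 3 of 16, 19 points) | SD, n = 20 | P(gap ≥ 4 of 20, 20 points) |
|---|---|---|---|---|
| 20% | 14.1 points | 26.5% | 12.6 points | 16.4% |
| 30% | 16.2 points | 33.3% | 14.5 points | 22.6% |
| 40% | 17.3 points | 36.7% | 15.5 points | 25.8% |
| 50% | 17.7 points | 37.7% | 15.8 points | 26.8% |

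**Step 2: what such a gap does to the HPR contrast.** This depends on carry-over from V1 to follow-up, for which the documents give no figure. Assume a follow-up HPR risk of 80% if V1-positive and 5% if V1-negative, the same in both arms. A 4-of-20 gap then shifts the crude difference by 0.20 × (0.80 − 0.05) = 15 points with no treatment effect. Weaker carry-over shrinks this in proportion.

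**Step 3: bias and type I error.** In simulation with no treatment effect (V1 HPR 20%, 35% and 50%; 16 and 20 per arm), the mean crude difference was within 0.002 of zero. The two-sided error was 1.7% to 2.5% for Fisher and 4.7% to 5.7% for Pearson. There is no bias to remove.

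**Step 4: precision.** Take 20 per arm, V1 HPR 35% and the risks of step 2.
- Overall risk: 0.65 × 0.05 + 0.35 × 0.80 = 0.3125. Crude SD: √(2 × 0.3125 × 0.6875/20) = 0.147 (simulated 0.145).
- Within-stratum variance: 0.65 × 0.05 × 0.95 + 0.35 × 0.80 × 0.20 = 0.0869. SD after stratifying: √(2 × 0.0869/20) = 0.093 (simulated 0.093).

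Stratification removes about 1 − 0.0869/0.2148 = 60% of the variance, where 0.2148 = 0.3125 × 0.6875.

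**Step 5: power.** Keep 20 per arm and V1 HPR 35%. Assume risks (V1-negative/V1-positive) of 5%/40% in A and 15%/90% in C. Crude rates are 0.65 × 0.05 + 0.35 × 0.40 = 17.25% and 0.65 × 0.15 + 0.35 × 0.90 = 41.25%, a true difference of 24 points.

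| Test | Unadjusted | Stratified by V1 HPR |
|---|---|---|
| Exact | Fisher 28% | Exact Mantel-Haenszel 44% |
| Large-sample | Pearson 40% | Cochran-Mantel-Haenszel 54% |

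The rows are the like-for-like comparisons. An exact stratified test is conservative and need not beat Pearson in every scenario. It matched or beat Fisher in every effect scenario tried, was about 2 points higher even when V1 status carried no information, and kept its type I error below 5%.

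**The case against.** The strongest reply is that nothing is biased. V1 HPR precedes randomization, and chance imbalance is already allowed for in the error rate of the Fisher and chi-square tests. That stands. A reader might infer that arm differences in HPR are confounded by prior non-response; the 1:1:1:1 allocation and step 3 do not support that. A reader might also infer that the entry criteria overlap with the HPR definition. They do not: entry requires clopidogrel use, not any level of reactivity, and HPR is defined as an on-treatment status, so counting everyone above the cut-off is what the definition asks for.

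It can also be said that V1 is one of the listed time points, so V1 HPR rates by arm would be reported and an imbalance would be visible. That is fair, but marginal rates neither adjust the test nor show individual transitions.

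The ANCOVA sentence, taken literally, covers every between-group comparison. It is, however, a general linear model with a reactivity value as covariate; categorical variables have their own sentence, and the baseline visit is unnamed. A V2 value, taken on ticagrelor, would not measure clopidogrel response. The text leaves the HPR adjustment undefined.

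Finally, V1 prevalence and carry-over are assumed, and V1 status need not predict HPR in group D. Both points stand: the gain concerns mainly the comparisons among A, B and C, and its size is uncertain.

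**Conclusion.** The point holds as a matter of efficiency and interpretation on a secondary endpoint. It does not touch the validity of the crude comparison or the primary PRU analysis. At 16 to 20 per arm, a V1 HPR gap of 19 to 20 points is expected in about 16% to 38% of two-arm comparisons, and the planned tests make no use of the measurement that would account for it. In the central scenario the exact test gains 16 points of power (28% to 44%). These figures rest on an assumed V1 HPR of 20% to 50% (35% in the power scenario) and on assumed follow-up risks by V1 status. If V1 status predicts little, the gain is small, but so is the cost. Separately, and whatever those values are, crude within-arm HPR rates cannot tell a return to the patient's own clopidogrel level from a rebound after the switch.

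**What to change.** In the Statistical analysis plan:

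1. Compare HPR between arms stratified by V1 HPR status, using the same assay and the same cut-off as the outcome (each of the two PRU cut-offs separately), with an exact Mantel-Haenszel test.
2. Keep reporting the crude HPR rates by arm and time point.
3. Tabulate V1 against follow-up HPR status by arm for each assay, as description only.
4. State that the baseline for this adjustment is V1, and name the visit that serves as baseline in the ANCOVA.

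Do not make new HPR (above the cut-off at follow-up but not at V1) a comparative endpoint. In the step 5 scenario it would reduce a 24-point difference to 0.65 × 15% − 0.65 × 5% = 6.5 points over all patients, because it drops the V1-positive patients, in whom that scenario's effect is largest.

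The cost is SAP wording and one cross-tabulation per assay; no visit or sample is added. The strata will be small, hence the exact method, and patients without a valid V1 value drop out of this secondary analysis.

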Version 6 August 21, 2017 NCT02287909

Pharmacodynamic evaluation of switching from ticagrelor to clopidogrel in patients

with coronary artery disease

[name], PhD, FACC, FESC, FSCAI Director of Cardiovascular Research Associate Professor of Medicine Division of Cardiology University of Florida College of Medicine - Jacksonville [name] [contact], [contact] [contact]

Project overview

The recommended antiplatelet treatment regimen for patients affected by acute coronary syndromes (ACS) and those undergoing percutaneous coronary intervention (PCI) consists in the combination of aspirin and a P2Y₁₂ receptor inhibitor. Currently, three P2Y₁₂ receptor inhibitors are available for clinical use (clopidogrel, prasugrel, and ticagrelor). Among these, clopidogrel remains the most widely used. However, recent studies have shown that there is a broad variability in platelet-inhibitory response induced by clopidogrel, which in turn is associated with worse outcomes. More potent $P2Y_{12}$ receptor inhibitors (prasugrel and ticagrelor) have been developed which are associated with less response variability than clopidogrel and better clinical outcomes. Ticagrelor use has increased significantly because of its more expanded Food and Drug Administration (FDA) indications compared with prasugrel. However, despite the evidence for sustained efficacy and safety, many physicians limit treatment duration with ticagrelor to the early phases following an ACS (early weeks or months, rather than one-year) mostly due to cost issues and concerns about increased bleeding. Therefore, it is very common in clinical practice to switch patients while on maintenance dosing (MD) with ticagrelor to treatment with clopidogrel. However, the pharmacodynamic (PD) effects of switching from ticagrelor to clopidogrel remain unknown. In addition, it is unknown whether switching from ticagrelor to clopidogrel should occur with or without a loading dose (LD). Therefore, the aim of this investigation is to evaluate the PD effects of switching from ticagrelor to clopidogrel with and without a LD. The present study has a prospective, randomized, open-label design, in which patients will be treated with 4 different strategies to assess PD profiling after switching. This study will provide important insights on PD effects of switching from ticagrelor to clopidogrel.

Background and Significance:

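### Repeated-measures ANOVA with no imputation, as normally run, drops partly complete patients from the intra-group and overall comparisons; paired tests or a mixed model would keep their valid samples

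*Combined protocol and SAP*

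**What the plan says.** The Statistical analysis plan gives two jobs to one method: "A repeated measures analysis of variance (ANOVA) model will be used to evaluate intra-group comparisons and the overall difference between groups". On incomplete data it says only "Missing data will not be imputed". It does not name the time points to be entered, an analysis set, or a rule for patients with some samples missing. The same section lists Student's t, Mann-Whitney and Wilcoxon tests for continuous variables, and SPSS v22.0 as the software.

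Other comparisons go elsewhere. A baseline-adjusted ANCOVA, "using the baseline value of platelet reactivity as a covariate, will be used to evaluate all between-groups comparisons". The primary endpoint is PRU at 48 h in group A against group C: "Superiority will be assessed using a 95% confidence interval (CI) of the difference in mean PRU between these two groups". The secondary endpoints are compared "in all four groups at each time points; rates of HPR according to each platelet function assay".

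The Blood sampling paragraph schedules seven samples per patient in groups B and D. Groups A and C have one more, after the 24 h washout: "these groups will have a total of 8 blood sampling time points". The sample size section allows for "a possible invalid data in 20-25% of patients due to technical issues or drop-outs" and randomises up to 80 patients in four equal arms.

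**The concern.** The usual repeated-measures ANOVA procedure needs a full row for each patient. With seven samples per patient and no imputation, one failed assay or missed visit removes the whole row. The plan expects incomplete data in a fifth to a quarter of patients but does not say what happens to them here.

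Two things are at stake. The intra-group time courses and the overall test would rest on fewer patients than have valid results, so they lose precision. A complete-case analysis is also valid only if incompleteness is unrelated to platelet reactivity within arm. A likelihood-based mixed model relaxes this to missing at random given the observed values. It does not help if missingness depends on reactivity that was never observed.

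**Working it through.** **Inputs.** From the documents: 16 per group required, 80 randomised 1:1:1:1, invalid data in 20–25% of patients, 7 common samples (8 in A and C). Assumed, because the documents do not give them: the pattern of missing samples, the within-patient correlation, and the SD on ticagrelor.

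**1. The plan's own figure.** 4 × 16 = 64 and 64/(1 − 0.20) = 80, so the total reproduces at 20% loss. At 25% loss, 80 × 0.75 = 60, or 15 per arm. The 16 per group is taken as given; its derivation does not bear on this point.

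**2. Patients and samples kept by complete-case ANOVA.** Read 20–25% as the share of patients with any invalid sample for an assay.
- Patients per arm: 20 × 0.80 = 16; 20 × 0.75 = 15.
- Equivalent independent loss per sample: 1 − 0.80^(1/7) = 3.1%; 1 − 0.75^(1/7) = 4.0%.
- Of 80 × 7 = 560 samples per assay, about 542 or 537 would be valid. The ANOVA would use 64 × 7 = 448 or 60 × 7 = 420. It discards about 94 (17%) or 117 (22%) valid samples.
- With 5% loss per sample: 20 × 0.95^7 = 14.0 per arm, or 20 × 0.95^8 = 13.3 if all eight samples are entered in A and C.

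**3. Analyses outside the problem.** An analysis that needs only the 48 h sample keeps 20 × (1 − 0.031) = 19.4 or 20 × (1 − 0.040) = 19.2 per arm. One that also needs a baseline value keeps 20 × (1 − 0.031)² = 18.8 or 20 × (1 − 0.040)² = 18.4. These small losses do not come from the repeated-measures model.

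**4. Gain from paired tests on available pairs.** If 4 or 5 patients per arm each lack one random sample, V2 against 48 h keeps 20 − 4 × 2/7 = 18.9 or 20 − 5 × 2/7 = 18.6 pairs. Relative to complete cases, the SE falls by 1 − √(16/18.86) = 7.9% or 1 − √(15/18.57) = 10.1%. With 5% loss per sample, 20 × 0.95² = 18.05 pairs remain and the reduction is 1 − √(13.97/18.05) = 12.0%.

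**5. Gain from a mixed model on all valid samples.** These are generalised least squares results for four arms of 20 and seven time points, with V1 and V2 means common to all arms, correlation 0.6 (assumed) and the covariance treated as known. The ranges span the within-arm change from V2 to 48 h and the mean post-randomisation A–C difference.

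| Missing pattern, per arm | SE reduction against complete cases |
|---|---|
| One sample each in 4 patients | 8.8–9.8% |
| One sample each in 5 patients | 11.6–12.5% |
| Drop-out from 24 h on, 4 patients | 6.4–7.4% |
| Drop-out from 24 h on, 5 patients | 8.5–9.5% |
| No post-randomisation sample in 2 of 4, 2 of 5 or 3 of 5 incomplete patients | 5.3–8.1% |
| No post-randomisation sample in any incomplete patient | 0–1.3% |
| 5% independent loss per sample | 14.7–14.9% |

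With the covariance estimated (simulated trials; 5 of 20 patients lacking one sample, or 5% loss per sample), a by-arm unstructured model reduced the empirical SE by about 11–16%. Available-pair tests reduced it by about 9–13%. The unstructured model's own SEs were 0.95–1.01 of the empirical ones. The model's advantage over paired tests is therefore only about 1–5%.

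**6. Choice of covariance.** V1 is on clopidogrel, V2 on ticagrelor, and the later samples in A–C follow the switch back to clopidogrel. A given lag between visits therefore mixes same-drug and cross-drug pairs. Suppose the correlation is 0.7 on the same drug and 0.4 across drugs, with SD 50 on clopidogrel and 40 or 25 on ticagrelor (all assumed except the 50). A by-arm heterogeneous Toeplitz structure then fits lag correlations of 0.60–0.65 where the true V2–48 h value is 0.4, and the SE of that change comes out 16–17% too small. A single-correlation structure (heterogeneous compound symmetry) gives SEs 3–8% too small. An unstructured matrix avoids this, at 7 × 8/2 = 28 parameters.

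**The case against.** The allowance of 20–25% is applied across all four arms, not only to A and C. At 20% it leaves the 16 complete patients per arm that the plan wanted. This stands as far as it goes: the loss was partly budgeted for. At 25% it leaves 15, and a budget for loss is no reason to discard results that are valid.

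The plan also lists t and Wilcoxon tests. If the intra-group comparisons are really meant as paired tests, most of the loss disappears and a mixed model adds only about 1–5%. This stands too, but the text assigns those comparisons to ANOVA, and paired tests do not supply the overall comparison.

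The size of the gain rests on assumptions. The documents give no per-sample loss, pattern or correlation, and the range reaches down to nearly zero. A mixed model with a convenient but wrong covariance can also make SEs too small, which would be worse than losing some precision. Both objections are right, and the second rules out the parsimonious structures in step 6.

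A reader might infer that the primary comparison loses patients in the same way. It does not: it needs the 48 h sample and at most a baseline value. Nor is the post-washout sample missing in B and D; it is scheduled only for A and C.

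**Conclusion.** The point holds as a modest improvement to secondary analyses. As normally run, the planned ANOVA would use 15–16 of 20 patients per arm if 20–25% of patients have any invalid sample for an assay. Using all valid samples would reduce SEs by roughly 5–15% under the assumed patterns. The gain is near zero in the four-arm model if incomplete patients give no post-randomisation sample.

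The 48 h A–C comparison and the HPR rates are outside the problem. So are the ANCOVAs, on one condition: that they are run separately at each time point. This is inferred from the wording of the secondary endpoints; the Statistical analysis plan does not say it. If the ANCOVA were fitted as a repeated-measures model with a covariate, the deletion would reach it as well.

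A reader might also infer that the complete-case results would be biased. Nothing in the documents shows that incompleteness is related to platelet reactivity, so only the loss of precision and the stronger missing-data assumption can be claimed.

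**What to change.** 1. Run the intra-group comparisons on all valid samples. Either name the paired tests on available pairs (for example V2 against each later time point), or fit a linear mixed model within each arm in SPSS MIXED with unstructured covariance.
2. Replace the overall repeated-measures ANOVA with a linear mixed model on all valid samples at the seven common time points (V1, V2, 2, 24, 48 and 72 h, 10±3 days), with unstructured covariance. Keep the post-washout sample of A and C out of the four-arm model; otherwise every B and D patient lacks a time point.
3. Keep the primary analysis and the ANCOVAs as planned, and state that the ANCOVAs are run per time point.
4. Do not use heterogeneous compound symmetry, or a heterogeneous Toeplitz model as a check on it.

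The cost is some SAP wording and modest programming in software already named. No visit, sample size or primary analysis changes. There are two statistical downsides. The by-arm model estimates 28 covariance parameters from 20 patients, so paired tests are the simpler choice there. The overall model estimates 28 from 80 patients and assumes one covariance for all arms, although the Project overview describes the newer agents, ticagrelor among them, as drugs "which are associated with less response variability than clopidogrel and better clinical outcomes". The planned ANOVA makes the same assumption.
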